3.1.1. Safety Review Team and Charter

An SRT will make decisions on initiating enrollment of higher dose cohorts and initiating the third dose of both investigational products based on available safety data in prior study cohorts as described in Section 3.1. There will be 3 planned SRT reviews in this protocol. Ad hoc reviews can be convened at the discretion of the SRT during the study based on new safety concerns and/or the protocol stopping rules (Section 3.3.3).

An SRT charter defining the team membership, meeting conduct, and decision-making process will be agreed upon by all team members before the first meeting. The data reviewed at the team meetings to make cohort transition decisions will be defined in the charter. The quality control checks performed on the data reviewed and used for making these decisions will also be described in the charter.

Source data verification may not be performed before SRT meetings. Alternative data quality control checks that are performed on data used to make dosing continuation or transition decisions are described in the SRT charter.

3.2. Duration of Dosing

The investigational product will be administered as a single agent or sequential injected doses as shown in [Table 8](#).

Table 8. Investigational Product Dose Timing

Cohort	1	2	3	4	8	5	6	7
Population	HP	HP	HP	HP	HP	CHB (Supp)	CHB (Supp)	CHB (Supp)
Dose Level	Low ^a	Low ^a	Low ^a	High ^b	High ^b	Low ^a	High ^b	High ^b
Study Day 1	GS-2829 or PBO IM	GS- -6779 or PBO IM	GS-2829 or PBO IM					
Study Day 29			GS-6779 or PBO IM					
Study Day 57	GS-2829 or PBO IM	GS-6779 or PBO IM	GS-2829 or PBO IM	GS-2829 or PBO IM	GS-2829 or PBO IM	GS-2829 or PBO IM	GS-2829 or PBO IM	GS-2829 or PBO IM
Study Day 85			GS-6779 or PBO IM					
Study Day 113					GS-2829 or PBO IM			GS-2829 or PBO IM
Study Day 141					GS-6779 or PBO IM			GS-6779 or PBO IM
Total number of doses (injections)	2	2	4	4	6	4	4	6

CHB = chronic hepatitis B; FFU = focus-forming unit; HP = healthy participant; IM = intramuscular; PBO = placebo;
Supp = suppressed

a Low dose = 0.5 mL of a 10-fold dilution of high-dose investigational product.

b High dose = 0.5 mL of high-dose investigational product ($\geq 1.0 \times 10^7$ FFU/mL).

All participants will be followed for safety for 6 months after their last dose of investigational product.

3.3. Protocol-Specific Discontinuation Criteria

GS-2829 and GS-6779 have been evaluated in nonclinical studies without any identified dose-limiting toxicity up to the highest proposed dose. In this first in human protocol, the following rules will guide early discontinuations from the study.

3.3.1. Criteria for Early Discontinuation for the Individual Participant From the Investigational Product

Administration of the investigational product should be discontinued in the following instances:

- If a participant experiences a Grade 3 or higher treatment-emergent AE (TEAE; excluding nausea, headache, measured grades of erythema and edema/induration alone) or confirmed Grade 3 or higher laboratory abnormality (except for those with a physiologic explanation for the events [eg, blood in urine occurring in a menstruating female, creatine phosphokinase elevation after strenuous exercise, triglyceride elevation that is nonfasting, etc]) considered clinically significant by the investigator and judged as related to the investigational product
- Any AE, laboratory abnormality or intercurrent illness which, in the opinion of the investigator, indicates that continued participation in the study is not in the best interest of the participant
- Participant request to discontinue for any reason
- Participant noncompliance
- Pregnancy during the study (refer to Appendix [11.4](#))
- Loss to follow-up
- Investigator discretion
- Discontinuation of the study by the sponsor

If a participant refuses to receive the remaining doses of investigational product as the result of an AE that is judged by the investigator as related to investigational product, an early termination (ET) visit should be completed, and every attempt should be made to retain the participant in the study to continue study evaluations. Following the receipt of any abnormal results believed to be related to investigational product at the ET visit, further testing should be repeated weekly or as often as deemed clinically appropriate by the investigator until the abnormality resolves, returns to baseline visit levels, or is otherwise explained.

If the participant withdraws consent from the study, the ET evaluations and/or procedures should be performed within 7 days of the decision to discontinue from the study.

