6.6. Assessments for Early Discontinuation From Investigational Product or From the Study

If a participant discontinues dosing with the investigational product (see Section [3.3](#)), for example as a result of an AE, the ET visit evaluation and/or procedures outlined in [Table 1](#), [Table 2](#), and [Table 3](#) should be performed within 7 days of last investigational product dose. If the last investigational product dose was received more than 7 days prior to decision to discontinue future dosing, the ET visit should be completed at the next scheduled study visit. Every attempt should be made to keep the participant on the study and continue to perform study-related follow-up and procedures. Evaluations indicating abnormal results believed to be related to investigational product at the ET visit should be repeated weekly or as often as deemed appropriate by the investigator until the abnormality resolves, returns to baseline visit levels, or is otherwise explained.

If a participant withdraws consent from the study, the ET visit will be their last study visit.

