7.7.2. Grades 3 Laboratory Abnormality or Clinical Event

- For a Grade 3 clinical event or clinically significant laboratory abnormality confirmed by repeat testing that is considered to be related to the investigational product (with the exception of ALT and AST elevations), the investigational product should be withheld until the toxicity returns to Grade 2 or below.
- If a laboratory abnormality recurs to Grade 3 or higher following rechallenge with the investigational product and this is considered related to the investigational product, then the investigational product should be permanently discontinued, and the participant managed according to local standard of care. Recurrence of laboratory abnormalities considered unrelated to the investigational product may not require permanent discontinuation.
- Detailed information on ALT elevation and flare management is provided in Section 7.7.4.

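### After a related, clinically significant Grade 3 event, Protocol Section 3.3.1 ends dosing while Section 7.7.2 only withholds it, and no visible text says which governs

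*Protocol*

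**What the plan says.** Protocol Section 3.3.1 sets the individual discontinuation criteria under the lead-in "Administration of the investigational product should be discontinued in the following instances". Its first criterion covers a Grade 3 or higher treatment-emergent AE ("excluding nausea, headache, measured grades of erythema and edema/induration alone") and a confirmed Grade 3 or higher laboratory abnormality ("except for those with a physiologic explanation for the events"), where the event is "considered clinically significant by the investigator and judged as related to the investigational product". The section has no provision to resume.

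Protocol Section 6.6 refers back to Section 3.3 and schedules the early termination (ET) visit. One branch begins "If the last investigational product dose was received more than 7 days prior to decision to discontinue future dosing", so discontinuation there means that later doses are not given.

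Protocol Section 7.7.2 covers a related Grade 3 clinical event, or a related and clinically significant Grade 3 laboratory abnormality confirmed on repeat, "with the exception of ALT and AST elevations". Its instruction is that "the investigational product should be withheld until the toxicity returns to Grade 2 or below". It then adds a rule that starts "If a laboratory abnormality recurs to Grade 3 or higher following rechallenge with the investigational product"; permanent discontinuation follows only if that recurrence is judged related. Section 7.7.3 requires a permanent stop at first occurrence for related Grade 4 events.

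Section 7.7 sends toxicities to the sponsor's medical monitor for discussion and points to Appendix 11.5 and to its own subsections. It does not mention Section 3.3.1, and Section 3.3.1 does not mention Section 7.7.

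**The concern.** This is a first-in-human trial, and Section 1.5 counts clear discontinuation parameters among its risk mitigations. Whether a participant with a related Grade 3 reaction is dosed again should follow from one rule. As written, an investigator who resumes dosing at Grade 2 complies with Section 7.7.2 and breaches Section 3.3.1.

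Participant protection is the main stake. The second is comparability: SAP Section 7.1.7.1 tabulates AEs leading to interruption and AEs leading to premature discontinuation separately, so the same clinical course could appear in either table depending on the section followed. Phase 1a runs at one site, so divergence between sites is mainly a matter for Phase 1b, with about 15 sites.

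**Working it through.** The plan states no figure on this point. The first check sets the rules side by side, for events judged related to product.

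| Event | Section 3.3.1 | Other section | Conflict? |
|---|---|---|---|
| (a) Grade 3 clinical event, clinically significant, outside the 3.3.1 exclusions and outside Section 1.5 | Discontinue | 7.7.2: hold to Grade 2 or below | Yes; resumption is implied |
| (b) Confirmed, clinically significant Grade 3 laboratory abnormality, not ALT/AST, no physiologic explanation | Discontinue | 7.7.2: hold; rechallenge contemplated | Yes; explicit |
| (c) Grade 3 nausea, headache, measured erythema or edema/induration alone; laboratory value with a physiologic explanation | Not triggered | 7.7.2: hold | No |
| (d) Hypersensitivity/anaphylaxis; potential immune-mediated condition | – | 1.5: stop product | Settled by 1.5 |
| (e) Grade 3 ALT/AST elevation | Not excepted | 7.7.2 does not apply; 7.7.4 does | Outside this point |
| (f) Grade 4, other than ALT/AST | Discontinue | 7.7.3: permanent stop | No |

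In rows (a) and (b), stopping for good satisfies both sections; resuming satisfies only Section 7.7.2. Section 7.7.2 cannot be read simply as an interim hold before Section 3.3.1 takes effect. Its laboratory trigger is already confirmed, related and clinically significant, and it still provides for rechallenge.

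The second check is how many doses depend on the choice. Inputs are the dose counts in Protocol Table 8 and 10 participants per cohort (Section 8.8).

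- Injections remaining after dose 1 of k: k − 1. Cohorts 1–2: 2 − 1 = 1. Cohorts 3–6: 4 − 1 = 3. Cohorts 7–8: 6 − 1 = 5.
- Dose spacing: 57 − 1 = 56 days in Cohorts 1–2; 29 − 1 = 28 days in Cohorts 3–8. An event back at Grade 2 before the next dose costs no dose under Section 7.7.2 and all remaining doses under Section 3.3.1.
- Planned injections: 20 × 2 + 40 × 4 + 20 × 6 = 40 + 160 + 120 = 320. Second or later: 20 × 1 + 40 × 3 + 20 × 5 = 20 + 120 + 100 = 240, and 240/320 = 75%. Placebo participants are included because sites are blinded and a placebo event can be judged related.

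The 240 is a ceiling: it counts every dose after the first.

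The third check is how far the cohort stopping rules limit the reach. Section 3.3.3 works in six units: Cohorts 1, 2, 3, 4+8, 5 and 6+7. In any unit, dosing is suspended by a second participant with a related Grade 3 or higher clinical AE of the same preferred term, or by a second participant with a related, confirmed, clinically significant Grade 3 or higher laboratory abnormality, subject to listed exceptions. In Phase 1a a single related SAE is enough. After suspension, the sponsor decides whether people already dosed finish the course; in Phase 1b the investigator and, where applicable, regulators share that decision. The conflict therefore mainly concerns the first participant per preferred term, or the first laboratory case, in each unit.

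**The case against.** The best case against is that this is a missing cross-reference with small consequences. Several parts of it stand.

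- Every toxicity goes to the medical monitor, which tempers divergence between sites. But Section 7.7 names no governing rule, so the discussion does not remove the conflict.
- The cohort rules take over at the second case. That stands and narrows the reach; it leaves the first case open.
- Appendix 11.5 may state precedence. In the text available it is only a heading, so its content cannot be treated as absent from the plan. This is why confidence is moderate.
- Section 7.7.2 makes redosing explicit only for laboratory abnormalities. That stands; for clinical events it is inferred from the temporary hold and from the contrast with Section 7.7.3.
- No dose is given at Grade 3 under either section, the SAP tables count recorded actions correctly, no formal testing is planned, and the primary endpoint is touched only through doses given. All of that stands.

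Three stronger readings are tempting and are not supported. A reader might take 240 of 320 injections as the exposure to the conflict; it is only an upper bound, and no event rate is given. A reader might infer that routine, short-lived vaccine reactions will often trigger it. The brief temperature rise in primates (Section 1.4) is ungraded, and Section 1.2.1.2 describes such findings as nonadverse, so it says nothing about related, clinically significant Grade 3 events in people. Finally, because Section 7.7.2 excepts ALT/AST, a reader might conclude that Section 3.3.1 should too. Table 11 covers only Cohorts 5–7, and the healthy-participant part of Section 7.7.4 has no permanent-stop rule. Such an exception would loosen protection in Cohorts 1–4 and 8, and at Grade 4 it would clash with Section 7.7.3.

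**Conclusion.** The concern holds for rows (a) and (b): two sections prescribe incompatible outcomes for the same event, and no visible text ranks them. The rule is contradictory as written, and the contradiction is worth correcting because it decides who receives further doses. After a first-dose event, 1, 3 or 5 injections depend on it. The number of participants affected cannot be estimated from the documents, and Section 3.3.3 keeps the reach mainly to first cases in six units.

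The conclusion rests on three assumptions: that discontinuation in Section 3.3.1 means ending dosing, as Section 6.6 indicates, although the word permanent is not used; that Appendix 11.5 does not already settle the matter; and that the qualifier on clinical significance and relatedness in Section 3.3.1 applies to clinical events as well as laboratory ones. If clinical significance is required only of laboratory abnormalities, the clinical-event conflict is wider. The documents do not show that anyone has been redosed contrary to Section 3.3.1, or that Section 7.7.2 requires redosing.

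**What to change.** Make Section 3.3.1 govern, as the more protective rule, and reword Section 7.7.2 along these lines: *A related Grade 3 event that meets Section 3.3.1 (ALT/AST elevations excepted, as now), or any hypersensitivity, anaphylaxis or potential immune-mediated condition under Section 1.5, leads to permanent discontinuation with an ET visit under Section 6.6. Holding product until Grade 2 or below, and any rechallenge, applies only to related Grade 3 events outside Section 3.3.1.*

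Check Appendix 11.5 and align it if it differs. Do not add an ALT/AST exception to Section 3.3.1. This leaves open how Section 3.3.1 and Section 7.7.4 fit together for ALT/AST.

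Optionally, show relatedness and action taken in the SAP listing of Grade 3 or higher AEs, and read the Grade 3 or 4 laboratory listing against the dosing listing, so that any redosing contrary to Section 3.3.1 can be seen.

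The cost is a wording amendment with ethics committee approval (Section 9.2.1) and a notice to sites; sample size, visit schedule and SAP tables are unchanged. The downside is that a participant with a brief related Grade 3 event loses the remaining doses, which Section 3.3.1 already requires.

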3.3.2. Criteria for Early Discontinuation for the Individual Participant From the Study

The participant will be discontinued from the study early in the following instances:

- Withdrawal of consent
- Participant request to discontinue for any reason
- Participant noncompliance
- Death

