Number of Participants Planned: Approximately 80 participants are planned for 8 cohorts. of 10 participants each: 50 healthy participants for Phase 1a activities and 30 participants diagnosed with CHB for Phase 1b activities.

Target Population:

Phase 1a: Healthy male and nonpregnant, nonlactating female participants, aged 18 through 60 years, inclusive

Phase 1b: Male and nonpregnant, nonlactating female participants diagnosed with CHB, aged 18 through 65 years, inclusive

Duration of Intervention:

- Cohorts 1 and 2 will receive 2 total doses over 56 days (Days 1 and 57).
- Cohorts 3, 4, 5, and 6 will receive 4 total doses over 84 days (Days 1, 29, 57, and 85).
- Cohorts 7 and 8 will receive 6 total doses over 140 days (Days 1, 29, 57, 85, 113, and 141).
- All participants will be followed for safety for 24 weeks following their last dose of investigational product (through Day 225 for Cohorts 1 and 2; through Day 253 for Cohorts 3, 4, 5, and 6; and Day 309 for Cohorts 7 and 8).

Diagnosis and Main Eligibility Criteria:

Phase 1a: Eligible participants will include those assigned male sex at birth or those who are nonpregnant, nonlactating, assigned female at birth, aged 18 through 60 years inclusive, with a body mass index (BMI) of $\leq 32.0 \text{ kg/m}^2$, with normal or nonclinically significant 12-lead electrocardiogram (ECG) evaluations, and no significant medical history. Participants will also be in good general health as determined by the investigator and have no prior history of hepatitis B virus (HBV) infection as demonstrated with a negative hepatitis B surface antigen (HBsAg) and hepatitis B core antibody test. Participants are prohibited from receipt of any investigational product or vaccine within 3 months of screening (with the exception of influenza and SARS-CoV-2 vaccines, which if needed, should be administered at least 14 days before or after an investigational product administration; participants should be encouraged to receive any needed vaccinations prior to enrollment) and should not receive ongoing therapy with any prohibited medications listed in the protocol.

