5.1.3. Procedures for Breaking the Blind on Treatment Codes

In the event of a medical emergency where breaking the blind is required to provide medical care to the participant, the investigator may obtain the treatment assignment for that participant from the IRT system. The sponsor recommends but does not require that the investigator contact the Gilead medical monitor before breaking the blind. Treatment assignment should remain blinded unless that knowledge is necessary to determine participant emergency medical care. The rationale for unblinding must be clearly explained in source documentation, along with the date on which the treatment assignment was obtained. The investigator is requested to contact the Gilead medical monitor promptly in case of any treatment unblinding.

Blinding of study treatment is critical to the integrity of this clinical study. Therefore, if a participant's treatment assignment is disclosed to the investigator, the participant will have study treatment discontinued. All participants will be followed until study completion unless consent to do so is specifically withdrawn by the participant.

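### Protocol Section 3.3.2 makes unqualified noncompliance a mandatory reason to leave the study, which conflicts with the protocol's own rules for keeping off-dose participants in safety follow-up

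*Protocol*

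**What the plan says.** Protocol Section 3.3.1 gives eight reasons to stop the investigational product. Section 3.3.2 gives four reasons to leave the study, under the lead-in "The participant will be discontinued from the study early in the following instances". Two entries are word for word the same in both lists: "Participant request to discontinue for any reason" and "Participant noncompliance". Section 3.3.2 lists withdrawal of consent as a separate entry.

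Other parts of the protocol speak for keeping people in follow-up:

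- **Section 3.3.1**, for participants who refuse further doses because of a related AE: "every attempt should be made to retain the participant in the study to continue study evaluations".
- **Section 6.6**, for any participant who stops dosing under Section 3.3, with an AE given only as an example: "Every attempt should be made to keep the participant on the study and continue to perform study-related follow-up and procedures". It makes the early termination visit the last one only where consent is withdrawn.
- **Section 4.1.1**: participants who received one of the two vectors and stop for reasons other than an AE may be replaced, but are encouraged to stay for safety evaluation.
- **Section 5.6.2**: when a participant cannot meet the listed restrictions, the investigator re-evaluates participation with the sponsor.
- **Section 5.1.3**, in the context of unblinding: "All participants will be followed until study completion unless consent to do so is specifically withdrawn by the participant".
- **Synopsis, Duration of Intervention**: "All participants will be followed for safety for 24 weeks following their last dose of investigational product". Section 3.2 says the same, expressed as 6 months.

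**The concern.** One event, noncompliance, triggers two rules that cannot both be followed. Under Section 3.3.1 it stops dosing, which brings in the Section 6.6 instruction to keep the participant on study. Under Section 3.3.2 it requires study exit. The exit rule is mandatory and the retention rule is best-effort, so a site reading both could reasonably let the exit rule prevail. Noncompliance is not defined in Section 3.3.2, so sites may also apply it differently.

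The primary endpoint is the proportion of participants with treatment-emergent AEs, SAEs and laboratory abnormalities. AEs are collected to 24 weeks after the last dose (Protocol Section 7.3.2). A dosed participant who is removed early stays in the Safety Analysis Set (SAP Section 3.1.2) but contributes no later non-serious AEs or scheduled laboratory results. SAP Section 3.6.1 does not in general impute missing data, and the SAP specifies no exposure-adjusted rate. Such a participant is therefore counted as event-free over time that nobody observed. In a first-in-human vector study, the participant also loses scheduled monitoring after exposure.

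**Working it through.** **1. Reproduce the planned follow-up.** Last dosing day and final visit come from the synopsis.

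| Cohorts | Last dose | Final visit | Difference |
|---|---|---|---|
| 1, 2 | Day 57 | Day 225 | 168 days |
| 3 to 6 | Day 85 | Day 253 | 168 days |
| 7, 8 | Day 141 | Day 309 | 168 days |

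168 / 7 = 24 weeks, which agrees with the stated figure.

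**2. Set the rules for noncompliance side by side.**

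| Protocol section | What follows | Force |
|---|---|---|
| 3.3.1 | product stops | should |
| 3.3.2 | participant leaves the study | will |
| 5.6.2 (listed restrictions) | participation re-evaluated with the sponsor | case by case |
| 6.6 (dosing stopped under 3.3) | keep on study, continue procedures | every attempt |
| Synopsis, 3.2 | safety follow-up for all after last dose | will |

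Sections 3.3.2 and 6.6 give opposite outcomes for the same participant.

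**3. Days lost by one removed participant (illustration).** Take a Cohort 7 participant dosed on Days 1 and 29 and removed for noncompliance on Day 57. Both vectors have been given, so the one-vector sentence in Section 4.1.1 does not apply.

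- Observed after last dose: 57 - 29 = 28 days.
- Lost from the 24-week period: 168 - 28 = 140 days, and 140 / 168 = 83%.

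**4. Weight of one participant.** The plan is 8 active and 2 placebo per cohort (Protocol Section 8.8).

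- Active column: 1 / 8 = 12.5%.
- Phase 1b placebo, pooled under SAP Section 3.2: 3 x 2 = 6, and 1 / 6 = 16.7%.

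These are shares of a column, not estimates of bias.

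**5. Effect on seeing a late non-serious event (illustration).** With n participants followed and a late-event probability p, the chance of at least one event is 1 - (1 - p)^n. The documents give no value for p, so a range is assumed.

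| Assumed p | 8 followed | 7 followed |
|---|---|---|
| 5% | 33.7% | 30.2% |
| 10% | 57.0% | 52.2% |
| 20% | 83.2% | 79.0% |

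Losing one of eight lowers the chance by 3.5 to 4.8 percentage points over this range.

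**6. What stays in the denominator.** TEAE summaries use the Safety Analysis Set, so one dose is enough. Laboratory abnormality summaries need one nonmissing postbaseline value (SAP Section 7.2.2.2). The participant in step 3 would be expected to meet both conditions.

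**The case against.** The protocol's intention to retain people is stated several times, and much of the safety information would survive an early exit. Section 7.3.3 asks for SAEs and deaths within 24 weeks of the last dose regardless of cause. Section 6.6 provides an early termination visit and repeat testing of related abnormal results. Section 7.7 asks that participants with AEs be monitored until the events settle or are explained. SAP Section 4.1 tabulates study discontinuation by reason, so shortened follow-up would be visible. The analysis is descriptive, with no formal testing. All of this stands and limits the loss to later non-serious AEs and scheduled laboratory results.

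Several stronger readings are tempting but are not supported:

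- **Only related-AE stoppers are kept and everyone else is removed.** Only two of the eight reasons in Section 3.3.1 recur in Section 3.3.2. Pregnancy, investigator discretion and unrelated AEs do not, and Section 6.6 covers anyone who stops dosing.
- **Declining further injections forces study exit.** Under its own heading, the request entry in Section 3.3.2 most naturally means a request to leave the study, which a site must honour. The identical wording in Section 3.3.1 makes it worth clarifying, but it is not a contradiction.
- **A missed dosing visit means removal.** Section 3.3.5 requires at least three contact attempts and allows three months before a participant is lost to follow-up. Section 6 treats departures from procedure as deviations to be recorded.
- **A participant stopped after a single injection in a two-vector cohort is lost.** For stopping unrelated to an AE, Section 4.1.1 already encourages that person to stay.

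None of this answers the conflict over noncompliance. The mandatory exit remains in Section 3.3.2 without a qualifier.

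**Conclusion.** The contradiction holds for noncompliance. Section 3.3.2 requires study exit for a reason that in Section 3.3.1 only stops product, against Sections 6.6 and 5.6.2, the synopsis and Section 3.2, and against Section 4.1.1 where it applies.

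For an affected participant the loss can be most of the planned follow-up (83% in the illustration), and one participant is 12.5% of a planned active column. The overall effect on the primary safety proportions cannot be estimated, because the documents give neither a noncompliance rate nor a late-event rate. A reader might infer that the design materially undercounts the primary endpoint. The documents do not show that. They show an avoidable route to missing data, with SAE and death reporting partly protected. The conclusion assumes that sites apply Section 3.3.2 as written and that the participant has not withdrawn consent.

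**What to change.** Reconcile Protocol Section 3.3.2 with Sections 3.3.1, 4.1.1, 5.6.2 and 6.6 and the synopsis:

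1. Remove noncompliance as an automatic reason for leaving the study in Section 3.3.2.
2. State that a participant request in Section 3.3.2 means a request to leave the study, that is, withdrawal of consent to further follow-up.
3. Apply the Section 6.6 retention sentence to every reason for stopping product, except withdrawal of consent, death, loss to follow-up and termination of the study. Cross-refer to it from Section 3.3.1, where the retention sentence now covers only refusals after a related AE.

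The criteria for stopping product stay as they are; the change concerns follow-up and data collection only. The cost is a short wording amendment and continued visits for the affected participants. Those visits are already in the schedules of assessments. The SAP needs no change.
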